**Additional Safety endpoints**

The incidence of all adverse events other than those listed in ISO 11979-7 (2018) tables E.3 and E.4.

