## 8.7.5 ADVERSE EVENT REPORTING

All AEs that occur during or after the Preoperative Visit through completion of study participation must be documented. Adverse events are collected from time of informed consent, and may be determined by evaluating the following in relation to the study subject:

- Observed or volunteered problems
- Complaints
- Physical signs and symptoms
- The occurrence of a medical condition during the study, which was absent at baseline
- The worsening of a baseline medical condition during the study

Each subject eye must be examined for the presence/absence of adverse events at all visits, whether scheduled or not. If an AE occurs, the first concern will be the safety and welfare of the subject; treatment should be provided as appropriate for the event.

AEs, regardless of causal relationship, must be assessed by the Investigator and recorded in the subject's CRF. AEs should be recorded in the form of a diagnosis, rather than signs and symptoms. Each AE must be described as ocular or non-ocular along with the following information: date of onset, date of resolution, severity, nature of the event (intermittent, continuous), action taken (none, medical and/or surgical), relationship to study device and surgical procedure, seriousness criteria and expectedness. Any medication or other intervention necessary for the treatment of an AE must be recorded on the appropriate eCRF. If the same type of AE occurs multiple times, each event should be recorded separately.

AEs will be documented beginning at the time of onset, and documentation must continue until recovery is noted. Events that are ongoing at the time of study exit should be followed until resolution or stabilization.

Ocular conditions or diseases noted during the Preoperative Visit that are chronic but stable and meet the inclusion/exclusions criteria should be recorded as Ocular History in the subject's case report form. The worsening of a preoperative condition or disease will be considered an AE. As applicable, signs and symptoms indicating a common underlying pathology should be noted as one comprehensive event.

---

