8.5.2 Additional Safety Endpoints and Analyses

The incidence of all adverse events, other than those listed in ISO 11979-7:2018 tables E.3 and E.4, will be summarized with number and percentage by test and control eyes. 90% confidence intervals (showing both lower and upper 5% boundaries) will be provided for incidence. Data will be provided in line listings.

SPE analyses will be provided for control eyes for completeness.

The incidence of loss of 10 letters or more of BCDVA between any two postoperative visits will be summarized with number and percentage by test and control eyes. Data will be provided in line listings.

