8.5.3 Adverse Event Reporting

The following definitions will characterize the nature of adverse events.

ADVERSE EVENT (AE)

An adverse event in this study is defined per ISO 14155:2020: Clinical investigation of medical devices for human subjects – Good clinical practice as any untoward medical occurrence, unintended disease or injury, or untoward clinical signs (including abnormal laboratory findings) in subjects, users or other persons, whether or not related to the investigational medical device. For this protocol, this definition includes events related to the comparator device(s) and/or the procedures involved.

ADVERSE DEVICE EFFECTS (ADE)

An adverse event related to the use of an investigational medical device or comparator device(s).

NOTE: This definition includes adverse events resulting from insufficient or inadequate instructions for use, deployment, implantation, installation, or operation; any malfunction; and use error or intentional misuse of the investigational or comparator(s) medical device.

DEVICE DEFICIENCY

Device deficiencies (ISO 14155:2020) related to the identity (e.g., labeling), quality, durability, reliability, safety, effectiveness, or performance of the study device must be reported to the Sponsor, or Sponsor's designee, within 7 days of the Investigator becoming aware of the deficiency. Device deficiencies must be recorded in the subject's case report form.

Device deficiencies will be categories as one of the following:

- **Device failure:** A device has failed if it is used according to the labeling, including without limitation, instructions for use, and applicable standards of medical practice but does not perform according to the labeling and negatively impacts the treatment.
- **Device malfunction:** A device malfunction is a change in the function of the device that is not described in the labeling and that may or may not affect device performance.

- **Device misuse:** A misused device, i.e., one that is not used by the Investigator (in the study) in compliance with applicable standards of medical practice, including without limitation, those described in the instructions for use and labeling, will not be considered a malfunction.
- **Other:** must be described by the Investigator

SERIOUS ADVERSE EVENT (SAE)

A serious adverse event (SAE) is defined as any untoward medical occurrence that meets any of the following:

- Requires inpatient hospitalization or prolongation of existing hospitalization;

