- Requires medical or surgical intervention to preclude permanent impairment of a body function or permanent damage to a body structure;
- Is life threatening (places the subject at immediate risk of death from the event as it occurred) or sight threatening;
- Results in permanent impairment of a body function or permanent damage to a body structure;
- Results in death
- May jeopardize the subject and require medical or surgical intervention to prevent one of the other outcomes.

UNANTICIPATED ADVERSE DEVICE EFFECT (UADE)

An unanticipated adverse device effect is defined per 21CFR 812.3(s) as any serious adverse effect on health or safety or any life-threatening problem, or death caused by, or associated with, a device, if that effect, problem, or death was not previously identified in nature, severity, or degree of incidence in the protocol or supplementary plan such as Clinical Investigator's Brochure, or any other unanticipated serious problem associated with a device that relates to the rights, safety, or welfare of subjects. Per this definition, UADE will be a subset of the SAEs reported in the study. UADEs are reportable per 21 CFR 812.3(s).

An investigator shall submit to the sponsor and to the reviewing Institutional Review Board (IRB) a report of any unanticipated adverse device effect occurring during an investigation as soon as possible, but in no event later than 10 working days after the investigator first learns of the effect.

NOTE: Vision-threatening (sight-threatening) adverse events are considered an UADE, reportable per 21 CFR 812.3(s) and must be reported to sponsor.

GENERAL COUNTING METHODS

A subject will be said to have experienced the occurrence of a given adverse event if either a pre-existing condition has worsened and requires prescribed medical treatment after IOL implantation, or a previously non-existent condition has developed after IOL implantation and

this new condition is deemed to be a clinically untoward event. The same adverse event cannot occur more than once unless it resolves prior to occurring again. Each occurrence corresponds to a unique preferred term. Adverse event resolution is as specified on the Adverse Event Form.

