A subject will be said to have experienced a persistent adverse event if a given adverse event is present at the conclusion of the clinical study (i.e., at database lock). The cumulative occurrence of an adverse event at an analytical time point refers to the total number of times a subject has experienced the occurrence of a given adverse effect between implantation and the conclusion of the clinical trial.

Incidence of adverse events (persistent or cumulative, as appropriate) listed in ISO 11979-7:2018 Table E.2 (Posterior chamber IOL adverse event rates will be compared to the historical control safety and performance endpoints (SPE) rates, as specified in **Section 7.5.1**. If none of the ISO-defined posterior chamber AE incidence rate is greater than the respective SPE rate, then investigational device will have met the co-primary safety endpoint on adverse event.

The AE tables will be listed by treatment group and will include the AE term, the event count, the incidence rate, and corresponding confidence intervals. The tables will be generated for the AEs listed in ISO 11979-7:2018, SAEs (separately for ocular and non-ocular), and all other AEs (separately for ocular and non-ocular). The table for the AEs listed in ISO 11979-7:2018 will also list *p*-values. The ocular AE tables may also be separately reported for device-related, procedure-related vs. non-related. If any UADE is reported in the study, they will be reported in a separate table.

Supplemental AE data listings will be ordered by subject and will list such information as AE term, treatment group, whether it is ocular or systemic, SAE (if applicable), date of onset, date of resolution, severity, relationship to the study device and relationship to the procedure. The onset of ocular adverse events will also be shown relative (in number of days) to the surgery date for that eye.

Per-subject data listings for death, SAEs, and premature discontinuation due to adverse events will also be produced.

Intraoperative adverse events are excluded from the above tables. An intraoperative AE is defined to be any adverse event with onset during surgery. Intraoperative adverse events will be presented in a data listing and summarized by treatment group.

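### The SAP's AE counting rule admits a worsened pre-existing condition only when it needs prescription treatment, contrary to the protocol and to the SAP's own AE definition, so untreated worsening could drop out of the AE tables

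*SAP*

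**What the plan says.** SAP 8.5.3, general counting methods, gives a two-limb rule. A subject has experienced an AE "if either a pre-existing condition has worsened and requires prescribed medical treatment after IOL implantation", or if a condition not present before has developed since implantation and is judged clinically untoward. Only the first limb asks for treatment.

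The SAP's AE definition, earlier in 8.5.3, asks for none. It covers "any untoward medical occurrence, unintended disease or injury, or untoward clinical signs (including abnormal laboratory findings) in subjects, users or other persons".

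Protocol 8.7.5 is direct: "The worsening of a preoperative condition or disease will be considered an AE". Among the details to be recorded for each AE it lists "action taken (none, medical and/or surgical", so none is a permitted value. The definition in Protocol 8.7.1 likewise has no treatment condition.

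The counts feed planned outputs. SAP 8.5.2 says: "The incidence of all adverse events, other than those listed in ISO 11979-7:2018 tables E.3 and E.4, will be summarized with number and percentage". SAP 8.5.3 adds: "The AE tables will be listed by treatment group and will include the AE term, the event count, the incidence rate", with confidence intervals, and provides a set of tables for "all other AEs (separately for ocular and non-ocular" events. Protocol 3.1 names as the additional safety endpoint "The incidence of all adverse events other than those listed in ISO 11979-7 (2018) tables E.3 and E.4".

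**The concern.** The protocol treats therapy as an attribute of an adverse event. The SAP's first limb turns it into a test for being one. A pre-existing condition that worsens and is simply watched, is managed with a non-prescription product, or is dealt with only surgically is an AE at the site but fails the SAP's rule.

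What is at stake is the completeness of the descriptive AE summary. A table described as covering all adverse events could omit events that investigators were required to report. A reader comparing tables with listings could then find differences that the SAP does not explain. Cases of this kind are foreseeable: Protocol 8.7.5 has stable chronic ocular conditions entered as ocular history and then treats their worsening as an AE.

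**Working it through.** The documents give no figure for this point and no rate of untreated worsening, so the check is a comparison of texts.

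1. **What each statement requires for a worsened pre-existing condition.**
   - Protocol 8.7.1: an untoward occurrence. Treatment is not mentioned.
   - Protocol 8.7.5: worsening is sufficient. It appears twice, once among the ways an AE may be identified and once as a flat statement. Action taken may be none.
   - SAP 8.5.3, AE definition: as broad as the protocol's.
   - SAP 8.5.3, counting rule: worsening and prescription medical treatment, joined by a conjunction.

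   Three statements agree and the counting rule stands alone.

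2. **Which statement governs.** SAP section 2 gives the SAP's analysis methods precedence over the protocol's. A programmer therefore cannot rely on Protocol 8.7.5 to override the counting rule. Within the SAP, nothing ranks the definition above the rule. No other section puts untreated worsening back into the counts.

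3. **Whether another rule explains the clause.** Protocol 8.7.7 exempts low-grade cells or flare, corneal edema and IOP rise in the first postoperative week, partly by reference to whether the medication regimen changed. That covers named, expected findings over a short period. It is not a general treatment condition for worsened pre-existing disease.

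4. **What is caught by another route.**
   - New conditions count under the second limb without treatment.
   - A 10-letter loss of BCDVA is an AE in its own right (Protocol 8.7.7) and has a separate summary by arm (SAP 8.5.2).
   - Secondary surgical interventions are a cumulative event (Protocol 8.7.2.1) and are analysed in SAP 8.5.1. Protocol 8.7.7 requires them and the events causing them to be reported whenever they occur.
   - SAEs have their own tables and per-subject listings, and UADEs a separate table (SAP 8.5.3).

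   What remains is mainly mild worsening that needs no prescription.

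5. **Effect on the ISO comparison.** It is probably small. Most of those events would be new after surgery, several relevant ocular conditions are excluded at entry (Protocol 5.2), and the persistent raised-IOP category already requires treatment (Protocol 8.7.2.2).

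6. **Scale of one omission.** SAP 6.2 plans 115 test eyes, so one omitted eye is 1/115 = 0.87 percentage points. This holds only within a single AE term, or for an eye with no other counted AE in the summary. The number of such eyes is unknown and may be zero.

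**The case against.** The strongest reply is that nothing important turns on the clause. The rule applies to both arms. No hypothesis is tested on the additional safety endpoint, and SAP 8.1 keeps additional analyses from supporting claims. The clinically serious forms of worsening reach the report by other routes, and SAP Appendix B promises line listings behind every summary table. All of this stands, and it is why the point is minor.

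A second reply is that the filter may never be applied. The AE attributes named in Protocol 8.7.5 include no flag separating a worsened condition from a new one, and none for prescription status. Treatments given for an AE are recorded, but applying the first limb would still mean matching events to medical history case by case, which the SAP does not describe. Tabulating every recorded AE is at least as plausible. This also stands as a reason for caution about the effect. It does not rescue the wording: if all recorded AEs are tabulated, the tables depart from the SAP's stated rule; if the rule is applied, recorded events are dropped.

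A reader might infer that the AE counts will be lower than the site records because of this clause. The documents do not support that. If every worsened condition receives prescription treatment, the clause removes nothing. Totals can also differ for an unrelated reason: sites collect AEs from consent, whereas the counting rule starts at implantation.

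A reader might also infer that the endpoint in Protocol 3.1 and SAP 8.5.2 covers only AEs outside the ISO list. Both texts exclude only tables E.3 and E.4, which the protocol synopsis uses as BCDVA references. The ISO adverse events are placed in Table E.2 by Protocol 9.9 and SAP 8.5.1.

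**Conclusion.** The conflict is real and rests on the wording alone. The counting rule is narrower than Protocol 8.7.1 and 8.7.5 and narrower than the definition in its own section, and the SAP does not say which prevails. Followed as written, it could leave untreated, non-prescription or purely surgical worsening out of the AE counts and incidence, and tables could disagree with site records and listings.

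The size cannot be derived from the documents and may be zero. A reader might be tempted to attach a percentage-point gap to the AE incidence. Any such figure would need assumed numbers of worsened eyes and an assumed treated share, and cases spread over several AE terms would not add up in one row.

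The consequence is descriptive and mainly concerns mild worsening. Data collection is not affected, because Protocol 8.7.5 still requires these events to be recorded. No co-primary decision is expected to change. Severity is minor; confidence is high for the mismatch in wording, not for any material undercount.

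**What to change.** In SAP 8.5.3, replace the first limb of the counting rule with: *a pre-existing condition has worsened after IOL implantation, whether or not it is treated (Protocol 8.7.5)*.

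If the sponsor wants to see the treated subset, show it as a separate row by action taken (none, medical, surgical).

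The cost is one clause in the SAP, to be changed before database lock. Action taken is already recorded for each AE, so no new data are needed, and the planned AE tables keep their structure apart from the optional row.

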#### Postoperative Adverse Events

- Anterior uveitis (including iritis and iridocyclitis)
- Capsular block syndrome
- Choroidal detachment/hemorrhage
- Chronic anterior uveitis [anterior segment inflammation characterized by grade 1+ cell or greater (using the Standardization of Uveitis Nomenclature [SUN] criteria) that is persistent for greater than 3 months after surgery, or relapses in less than 3 months after discontinuation of therapy, or the subject is maintained on therapy for more than 3 months to control inflammation.] Note that any iritis present at the final visit is considered significant and should be counted as a 'persistent ISO SPE event'.
- Visually significant corneal edema [corneal swelling (stromal or epithelial) resulting in BCDVA of 0.3 logMAR or worse at Form 3 or later]. Note that any corneal stromal edema present at the final visit is considered significant and should be counted as a 'persistent ISO SPE event'.
- Clinically significant cystoid macular edema (CME) diagnosed by clinical exam and adjunct testing (e.g., OCT or other method), resulting in BCDVA of  $\leq 0.3$  logMAR at Form 3 or later
- Endophthalmitis (intraocular inflammation leading to diagnostic vitreous tap and use of intraocular antibiotics)
- Flat anterior chamber with lens/cornea touch or a shallow chamber with iridocorneal apposition without lens/cornea touch
- Anterior Capsular Contraction Syndrome (ACCS, Phimosis)
- Hypopyon
- Corneal endothelial damage
- Incorrect IOL power resulting in secondary surgical intervention
- Increased IOP (elevation of IOP  $\geq 10$  mmHg above the IOP measured at the Preoperative Visit to a minimum of 25 mmHg)
- Infectious keratitis
- IOL damage resulting in secondary surgical intervention

- IOL dislocation, tilt, decentration, luxation, rotation resulting in secondary surgical intervention
- Best-corrected distance visual acuity loss of 2 lines (10 letters) or more on the ETDRS chart measured at or after postoperative Form 4 compared to any prior postoperative visit
- Best-corrected distance visual acuity loss of 2 lines (10 letters) or more since the prior visit
- Mechanical pupillary block (A shallowing of the anterior chamber due to obstruction of aqueous humor flow from the posterior to anterior chamber through the pupil by the crystalline lens, vitreous face, or implanted device)

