8.5.1 Co-Primary Safety Endpoints and Testing

1. Cumulative rate of SSIs related to the optical properties of the IOL at Form 4, including IOL rotation SSIs for misalignment.
2. Rates of cumulative and persistent AEs at Form 4 via comparison to the ISO Safety and Performance Endpoint (SPE) rates as described in ISO 11979-7:2018.
3. BCVA logMAR of 0.3 or better at Form 4 for all-implanted and best-case test eyes.

[REDACTED] of the observed proportion is compared with the maximum allowable SPE rate. If the lower boundary of the confidence interval does not exceed the SPE rate, then the endpoint will meet the success criterion. For safety co-primary endpoint 1, the rate of SSIs related to the optical properties of the IOL will be analyzed separately in addition to overall analysis. A 95% Clopper-Pearson confidence interval will be provided for the rate of SSIs related to the optical properties of the IOL; however, this rate will not be compared to the ISO historical SPE rate. The total SSI rate, including both rotation-related and non-rotation-related SSIs, will be compared to the corresponding ISO SPE rate.

[REDACTED] The number of eyes (in the safety population) with event present at any time and the number of eyes in the safety population are included for cumulative events. For persistent events, the number of eyes with the event present at Form 4 and the number of eyes present at the Form 4 visit are included without imputation. Cumulative and persistent events will be provided for the study eye and fellow eye.

[REDACTED] For All-Implanted, the rate used for the analysis is the number of eyes with the required level measured at Form 4 and the number of eyes present at the Form 4 visit without imputation. For Best Case, the rate used for the comparison to the ISO SPE historical rate should be defined as the number of Best Case eyes with the required acuity level at Form 4 and the number of Best Case eyes present at Form 4. The analysis will be provided for the study eye. [REDACTED]

[REDACTED]

[REDACTED]

[REDACTED]

More generally stated, for each type of adverse event listed in ISO 11979-7:2018 Table E.2, the rate for the test eyes is not statistically greater than the SPE rate for that event. The comparison between the adverse event rate for the test eyes and the SPE rate for posterior chamber IOL for each adverse event will be performed using the exact test based on binomial distribution at $\alpha = 0.10$ (one-sided).

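### SAP 8.5.3 and SAP 8.5.1 define persistent and cumulative events differently, so the counts for co-primary safety endpoint 2 have two incompatible definitions

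*SAP*

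**What the plan says.** **Persistent events.** SAP 8.5.1 sets the rate as "the number of eyes with the event present at Form 4 and the number of eyes present at the Form 4 visit", without imputation. SAP 8.5.3, under its general counting methods, instead calls an event persistent if it is "present at the conclusion of the clinical study (i.e., at database lock", and gives no denominator.

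**Cumulative events.** SAP 8.5.1 uses this numerator: "The number of eyes (in the safety population) with event present at any time". The denominator is all eyes in that population. SAP 8.5.3 says that cumulative occurrence "refers to the total number of times a subject has experienced the occurrence of a given adverse effect", from implantation to the end of the trial. The same section lets an event count again once it has resolved.

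**Link to the endpoint.** Directly after its definitions, SAP 8.5.3 says that persistent or cumulative incidence, as applicable, will be compared with the SPE rates, and states when the device meets the adverse-event co-primary. For the method it points to Section 7.5.1. Section 7 of the SAP stops at 7.2.1.

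**Protocol.** Section 8.7.2.1 reports a total of the listed events at any time. Section 8.7.2.2 takes those present when the investigation concludes. Section 8.7.7 is more specific: "Note that any iritis present at the final visit is considered significant", with a matching note for corneal stromal edema. The protocol never ties persistence to database lock. Its section 4.3 defines the end of the study by the last procedure of the last visit.

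**The concern.** Co-primary safety endpoint 2 is decided by comparing small counts with SPE limits, and SAP 8.5 requires every co-primary safety endpoint to be met. Each count needs one definition, fixed before the data are seen.

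The two sets of rules can give different counts from the same data. Protocol 8.7.5 says: "Events that are ongoing at the time of study exit should be followed until resolution or stabilization". An event present at Form 4 may therefore have resolved by lock. The same section has repeat events recorded separately, so one eye can contribute several occurrences.

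There is also a problem of form. SAP 8.5.1 specifies an exact binomial test, which needs one yes/no outcome per eye. A tally of occurrences is not a binomial count. Lock status, for its part, is observed after a different length of time for each subject.

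**Working it through.** **1. Denominators.** SAP 6.2 plans 115 test and 115 control eyes and expects 13% of the 230 not to complete, leaving 200. Check: 230 × (1 − 0.13) = 200.1, which reproduces the stated figure. If attrition is equal between arms, about 100 test eyes reach Form 4. So n is about 115 for cumulative events (taking the Safety population as about 115 test eyes) and about 100 for persistent events. Only one eye per subject is in the study, so for the study eye the difference is not subject against eye. It is eyes ever affected against number of occurrences.

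**2. Time from Form 4 to lock.** The protocol synopsis gives 8 months of enrollment, 9 months of participation and 3 months for close-out, lock and report.
- Last subject's Form 4: up to month 8 + 9 = 17.
- Lock: between month 17 and month 17 + 3 = 20.
- Earliest possible Form 4: day 120 after surgery, about month 4.
- Gap for the last subject: 0 to 3 months.
- Gap for the earliest subject: 17 − 4 = 13 to 20 − 4 = 16 months. This is an upper extreme, because it pairs the earliest Form 4 with the longest timeline.

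**3. Pass rule.** The endpoint passes if the exact one-sided lower limit L for x events in n eyes does not exceed the SPE rate. L is the α quantile of a beta distribution with parameters x and n − x + 1; for x = 1 this is 1 − (1 − α)^(1/n). SAP 8.5.1 states both α = 0.10 one-sided and a one-sided 95% limit, so both are shown.

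| x/n | L at α = 0.05 | L at α = 0.10 |
|---|---|---|
| 1/115 | 0.045% | 0.092% |
| 2/115 | 0.310% | 0.463% |
| 3/115 | 0.715% | 0.962% |
| 1/100 | 0.051% | 0.105% |
| 2/100 | 0.357% | 0.533% |

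**4. Effect at an assumed SPE of 0.3%.**
- Cumulative: one eye has two episodes. Per eye this is 1/115, which passes. Per occurrence it is 2/115, which fails (narrowly at α = 0.05: 0.310% against 0.3%).
- Persistent: two eyes have the event at Form 4. That is 2/100, which fails. If one resolves before lock, the count becomes 1/100, which passes.

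Both reversals occur at either α.

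**5. Effect over an assumed SPE range of 0.1% to 3%.** Largest count that still passes:

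| Assumed SPE | n = 115, α 0.05 | n = 115, α 0.10 | n = 100, α 0.05 | n = 100, α 0.10 |
|---|---|---|---|---|
| 0.1% | 1 | 1 | 1 | 0 |
| 0.3% | 1 | 1 | 1 | 1 |
| 0.5% | 2 | 2 | 2 | 1 |
| 0.8% | 3 | 2 | 2 | 2 |
| 1% | 3 | 3 | 3 | 2 |
| 2% | 5 | 4 | 5 | 4 |
| 3% | 7 | 6 | 6 | 5 |

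A single eye with three episodes, counted per occurrence, fails by itself at 0.5% and below. At 0.8% it fails only at α = 0.10, and at 1% it passes. At higher rates one extra event matters only if the count is already at the limit.

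**6. Direction.** Occurrences are never fewer than affected eyes, so occurrence counting can only raise the cumulative count. Lock status can lower the persistent count, when an event resolves after Form 4. It can also raise it, when an eye left before Form 4 with an unresolved event and so does not appear in the 8.5.1 count.

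**The case against.** The strongest reply is that SAP 8.5.1 governs. It is the section on testing this endpoint, it gives explicit numerators and denominators, and 8.5.3 sets no competing test. The pointer to 7.5.1 is one of several stale numbers: SAP 7.2.1 cites 7.4.3 and SAP 8.2 cites 7.5.3. The SPE sentence in 8.5.3 speaks of incidence, and its tables list event counts and incidence rates as separate items. Apart from the mention of lock, much of 8.5.3 follows Protocol 8.7.2.1 and 8.7.2.2.

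Most of this stands. A reader might infer that the SPE counts are already corrupted, or shifted in the device's favour. The documents do not support either inference. The natural reading keeps the counts per eye and at Form 4, and the two 8.5.3 rules do not share a direction.

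The reply does not remove the conflict. The definitions in 8.5.3 come immediately before its statement of when the co-primary is met, and the section it relies on does not exist under that number. No visible text says which section prevails, although redacted text in 8.5.1 might. The protocol cannot settle the matter, because SAP section 2 says the SAP's methods supersede the protocol's.

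**Conclusion.** The SAP is wrong as written: it defines each of the two counts behind co-primary safety endpoint 2 in two incompatible ways. That rests on the text alone.

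The size depends on assumptions. With about 115 and 100 test eyes and an assumed SPE of 0.3%, one event reverses pass and fail for either type of count. Across the assumed range of 0.1% to 3%, the largest passing count runs from 0 or 1, depending on α, up to 7, so the effect is strongest at low rates. What is shown is a result left open to a choice of definition after the data are seen, not a biased result.

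The two values of α in SAP 8.5.1 are a separate matter that also needs reconciling. They do not change the examples at 0.3%.

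**What to change.** In SAP 8.5.3:
- Delete the parenthesis that equates study conclusion with database lock. Define persistent events as eyes with the event present at Form 4, over eyes present at Form 4.
- For the SPE test, define cumulative events as eyes with at least one occurrence at any time through Form 4, over Safety-population eyes. Match the start of counting to that population. Implantation is not a suitable start, because Protocol 5.3 places in the Safety population eyes that the lens touched but that did not keep a study lens.
- Keep occurrence counts as a descriptive column only.
- List eyes that left before Form 4 with an unresolved event, since the Form 4 rate cannot include them.
- Correct the cross-reference from 7.5.1 to 8.5.1.

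The cost is SAP wording only, with no new data. Compared with lock status, persistent counts may be slightly higher. The change should be made before lock and before anyone sees results by arm.
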